3 OBJECTIVES AND ENDPOINTS

3.1 Objectives, Hypotheses, and Estimands

Primary Objective

The primary study objectives are:

- Sub-Study 1 (SS1): The primary study objective for SS1 is to evaluate the efficacy and safety of dose escalation to upadacitinib 30 mg QD in subjects who do not achieve EASI 90 on upadacitinib 15 mg QD after 12 weeks.
- Sub-Study 2 (SS2): The primary study objective for SS2 is to evaluate the efficacy and safety of
 dose reduction to upadacitinib 15 mg QD in subjects who achieve EASI 90 on upadacitinib 30 mg
 QD after 12 weeks.

No hypothesis testing will be performed in this study.

The estimand corresponding to the primary endpoint is defined as:

 The proportion of subjects who achieve EASI 90 at Week 24, regardless of treatment discontinuation, with upadacitinib treatments (upadacitinib 15 mg or 30 mg QD) in adult subjects with moderate to severe AD.

Additional Objective

• To generate evidence on patient impact (patient reported outcomes [PROs]) with upadacitinib treatment based on a clinical response target (EASI 90) (Treat-to-Target).

This study will generate descriptive data that will provide information regarding:

- Efficacy and safety of dose escalation to upadacitinib 30 mg QD in subjects that did not achieve EASI 90 on upadacitinib 15 mg QD after 12 weeks.
- Efficacy and safety of dose reduction to upadacitinib 15 mg QD in subjects that achieve EASI 90 on upadacitinib 30 mg QD after 12 weeks.
- The effect of a treat-to-target approach based on EASI 90 response for subjects' reported itch, sleep, emotional health, and quality of life [QoL].

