5.7 Study Drug

The individual study drug information is presented in Table 2.

Table 2. Description of Study Drug

	Investigational Product	Investigational Product
Investigational product name	upadacitinib	upadacitinib
Mode/Route of Administration (ROA)	Oral	Oral
Formulation	15 mg	30 mg
Dosage Form	Extended-release tablets	Extended-release tablets
Masking	Blinded	Blinded
Frequency of administration	QD	QD
Manufacturer	AbbVie	AbbVie

QD = once daily

Upadacitinib will be taken orally once daily, beginning on Day 1 (Baseline) and can be taken with or without food. Upadacitinib should be taken whole and should not be split, crushed, dissolved, etc. If subjects should forget to take upadacitinib at their regularly scheduled dosing time, they should take the forgotten dose as soon as they remember as long as it is at least 10 hours before their next scheduled dose. Otherwise, they should take the next dose at the next scheduled dosing time.

The subject will be instructed to return all drug containers (even if empty) to the study site personnel at each study visit. The study site personnel will document compliance.

AbbVie will provide upadacitinib. AbbVie-provided study drug should not be substituted or alternately sourced unless otherwise directed by AbbVie.

AbbVie will not supply drug other than upadacitinib. Subjects will continue their AD disease-related concomitant medications therapy as allowed per protocol. AbbVie will not supply any AD disease-related concomitant medication therapy taken during the study.

Study drug will be packaged in quantities sufficient to accommodate study design. Each kit will be labeled per local requirements, and this label must remain affixed to the kit. Upon receipt, study drug should be stored as specified on the label and kept in a secure location. Each kit will contain a unique kit number. This kit number is assigned to a subject via Interactive response technology (IRT) and encodes the appropriate study drug to be dispensed at the subject's corresponding study visit. All blank spaces on the label will be completed by the site staff prior to dispensing to subjects. Study drug will only be used for the conduct of the study.

During the COVID-19 pandemic, study drug shipment can be made from the study site to the subject if allowed by local regulations. Refer to the Operations Manual for details on direct-to patient shipment of study drug (Appendix F).

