# Analysis of Quantitative Laboratory Parameters (Hematology, Chemistry and Urinalysis)

Raw values and change from Baseline (percent change if applicable) to each applicable post-baseline visit will be summarized for selected laboratory variables in the Safety 1 and Safety 2 Populations. At each visit, the following descriptive statistics will be presented by treatment groups: number of observations, Baseline mean (Standard deviation, SD), visit mean (SD), medium, change from Baseline mean (SD), standard error, and the 95% confidence interval of the mean change from Baseline.

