#### **Shift Table Analyses**

Selected laboratory parameters will be tabulated using shift tables from Baseline to the worst value by NCI CTCAE in DB Period for the Safety 1, in SB Period for the Safety 2 Population and during the administration of upadacitinib for the All UPA Population.

Selected lipid parameters will be summarized using National Cholesterol Education Program (NCEP) Adult Treatment Panel III (ATPIII) guidelines and details can be found in Appendix E. Similar shift tables will be provided to summarize shifts from Baseline to the final post-baseline value in DB Period for the Safety 1, in SB Period for the Safety 2 Population and during the administration of upadacitinib for the All UPA Population. Here, the Upadacitinib Baseline is defined as the last observation prior to the first dose of upadacitinib. The criteria in shift table are defined using CTCAE 4.03.

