### 10.4 Analysis of Vital Signs

Vital sign measurements of systolic and diastolic blood pressure, pulse rate, respiratory rate and body temperature will be summarized.

Each vital sign variable will be summarized for all time points (starting with Baseline) with the number of non-missing observations, mean and standard deviation, median, minimum and maximum. Mean change from Baseline to each applicable post-baseline visit in both DB Period and SB Period will be summarized for each vital sign variable, with the number of observations, Baseline mean, and visit mean. The change from Baseline mean, standard error, and 95% confidence interval will be presented for the mean change from Baseline within each treatment group in Safety 1 and Safety 2 Populations.

Vital sign variables will be evaluated based on potentially clinically important (PCI) criteria (Appendix D) for the Safety 1, Safety 2 and the ALL UPA Population. For each vital signs PCI criterion, the number and percentage of subjects who have at least one vital sign value meeting the criteria will be summarized. Listings will be provided to summarize subject-level vital sign data for subjects meeting PCI criteria.

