#### Appendix D. Potentially Clinically Important Criteria for Safety Endpoints

The criteria for Potentially Clinically Important (PCI) laboratory findings are described in Table D-1 and Table D-2, PCI criteria for the liver function tests are described in Table D-3, and the PCI criteria for vital sign findings are described in Table D-4.

Table D-1. Criteria for Potentially Clinically Important Hematology Values

		Definition of Potentially Clinically Important
Hematology Variables	Units	Very Low
Hemoglobin	g/dL	< 8.0
Platelets count	$10^{9}/L$	< 50.0
WBC count	$10^{9}/L$	< 2.0
Neutrophils	$10^{9}/L$	< 1.0
Lymphocytes	$10^{9}/L$	< 0.5

Table D-2. Criteria for Potentially Clinically Important Chemistry Values

[figure not shown]
		Definition of Potentially Clinically Important	
Chemistry Variables	Units	Very Low	Very High
ALP	U/L		> 5.0 × ULN
SGOT/AST	U/L		$> 5.0 \times ULN$
SGPT/ALT	U/L		$> 5.0 \times ULN$
Albumin	g/L	< 20	
Glucose	mmol/L	< 2.2	> 13.9
Triglycerides	mmol/L		> 5.7
Creatinine	mcmol/L		$> 3.0 \times ULN$
Potassium	mmol/L	< 3.0 > 6.0	
Calcium	mmol/L	< 1.75	> 3.1
Sodium	mmol/L	< 130	> 155
Phosphate	mmol/L	< 0.6	
CPK	U/L		$> 5.0 \times ULN$
Total Cholesterol	mmol/L		> 10.34

**Table D-3.** Criteria for Potentially Clinically Important Liver Function Tests

		Definition of Potentially Clinically Important	
Variables	Units	Very High	
AST	U/L	$\geq$ 3 × ULN	
		$\geq$ 5 × ULN	
		$\geq 10 \times \text{ULN}$	
		$\geq$ 20 × ULN	
ALT	U/L	$\geq 3 \times ULN$	
		$\geq$ 5 × ULN	
		$\geq 10 \times \text{ULN}$	
		$\geq$ 20 × ULN	
Total Bilirubin	UMOL/L	$\geq 2 \times ULN$	
Alkaline phosphatase	U/L	$\geq$ 1.5 × ULN	
ALT (U/L) and/or AST (U/L)	ALT and/or AST $\geq$ 3 × ULN and concurrent TBL		
and concurrent TBL		$\geq 1.5 \times \text{ULN}$	
(UMOL/L)		ALT and/or AST $\geq$ 3 × ULN and concurrent TBL	
		$\geq 2 \times ULN$	

Table D-4. Criteria for Potentially Clinically Important Vital Sign Values

Vital Sign	Category	Criteria for Potential Clinically Significant Vital Signs
Systolic blood pressure	Low	Value ≤ 90 mmHg and decrease ≥ 20 mmHg from Baseline
	High	Value ≥ 160 mmHg and increase ≥ 20 mmHg from Baseline
Diastolic blood pressure	Low	Value ≤ 50 mmHg and decrease ≥ 10 mmHg from Baseline
	High	Value ≥ 100 mmHg and increase ≥ 10 mmHg from Baseline
Pulse	Low	Value ≤ 50 bpm and decrease ≥ 15 bpm from Baseline
	High	Value ≥ 120 bpm and increase ≥ 15 bpm from Baseline
Weight (adults)	High	> 7% increase from Baseline
	Low	> 7% decrease from Baseline

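### Single-blind laboratory, vital-sign and weight displays are referenced to a pre-treatment Baseline, and none is planned for change since the Week 12 dose switch

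*SAP*

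**What the plan says.** Protocol 3.1 lists among the information the study will provide: "Efficacy and safety of dose escalation to upadacitinib 30 mg QD in subjects that did not achieve EASI 90 on upadacitinib 15 mg QD". The SS2 counterpart is the safety of reducing to 15 mg.

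The SAP plans these single-blind (SB) safety displays:

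- **Laboratory means (SAP 10.3, quantitative parameters):** change from Baseline "to each applicable post-baseline visit will be summarized for selected laboratory variables in the Safety 1 and Safety 2 Populations".
- **Laboratory shifts (SAP 10.3, Shift Table Analyses):** "shift tables from Baseline to the worst value by NCI CTCAE in DB Period for the Safety 1, in SB Period for the Safety 2". Lipid shifts run from Baseline to the final value in each period. The lipid paragraph adds: "Here, the Upadacitinib Baseline is defined as the last observation prior to the first dose of upadacitinib".
- **Vital signs (SAP 10.4):** "Mean change from Baseline to each applicable post-baseline visit in both DB Period and SB Period will be summarized for each vital sign variable".
- **PCI criteria (SAP Appendix D):** Table D-4 defines the blood pressure, pulse and weight criteria wholly or partly as change from Baseline; for weight gain in adults the rule is "> 7% increase from Baseline". Tables D-1 to D-3 are absolute laboratory limits.

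Protocol 7.5 also plans laboratory and vital-sign mean change from Baseline within each period. For adverse events the rule differs: under SAP 10.2.1 an event belongs to the SB Period only if it starts or gets worse once SB dosing has begun.

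**The concern.** The SB Period exists to show what happens after the switch. Adverse-event counts restart there, but the measured safety variables do not. A laboratory shift that arose on the first dose and persists appears again in the SB table under the new dose group: 15/30 if it arose on 15 mg, 30/15 if it arose on 30 mg. The absolute laboratory PCI limits raise a related problem. SAP 10.3 counts any subject with a qualifying value in the period and states no new-onset rule, so a value already beyond the limit at Week 12 that persists is counted again.

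At stake is whether a reader can tell, for these measures, what followed the dose change and what was already there.

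**Working it through.** **1. Which Baseline applies?** The sentence quoted from the lipid paragraph is explicit but local. Three other places point the same way:

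- The opening of SAP 10.3, which governs all laboratory data, ties Baseline to assessments on or before the first dose of study drug.
- Protocol 5.7 equates Day 1 with Baseline.
- Where the SAP means the start of the SB Period it says so (SAP 6.0, 7.2 and 10.2.1). It attaches no such qualifier to Baseline in 10.3, 10.4 or Appendix D.

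The only use of Week 12 as a reference is an efficacy one, the loss-of-response endpoint in SAP 3.3. The pre-treatment reading is therefore firm for the lipid shifts and a well-supported inference for the rest.

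**2. Can the post-switch change be recovered from the planned tables?** In SAP Table 1 the Safety 1 groups are 15 mg and 30 mg only; the four cohorts exist only in Safety 2. Subtracting a Safety 1 Week 12 mean from an SB cohort mean compares different sets of subjects. If Week 12 means were shown by cohort, which is not stated, the mean change would follow by subtraction, but its CI would not, because that depends on the within-subject correlation r. With equal SDs the half-width in SD units is 1.96 × √(2(1 − r)/n). Take n = 227 × 0.54 × 0.92² = 103.8, about 104 in SC1, using the SAP 2.4 assumptions and half of 454. The half-width is then 0.21, 0.17 and 0.12 for r = 0.4, 0.6 and 0.8. Shifts since Week 12 cannot be recovered from summary tables at all.

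**3. How large could the difference be?** The plan gives no figure to reproduce. All effect sizes below are assumptions.

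*Means.* Suppose the effect is dose-dependent and reversible, with a plateau by Week 12. Then change from Day 1 = effect of the current dose, and change from Week 12 = effect of the current dose − effect of the previous dose.

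| Assumed effect, 15 / 30 mg | SC1 from Day 1 | SC1 from Week 12 | SC4 from Day 1 | SC4 from Week 12 |
|---|---|---|---|---|
| +5 / +10 | +10 | 10 − 5 = +5 | +5 | 5 − 10 = −5 |
| +10 / +15 | +15 | 15 − 10 = +5 | +10 | 10 − 15 = −5 |
| +10 / +20 | +20 | 20 − 10 = +10 | +10 | 10 − 20 = −10 |

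The ratio for SC1 (2, 3 and 2) depends wholly on the pair chosen.

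*Shifts.* Simulate a normal marker with a category limit 1 SD above the pre-treatment mean, r from 0.6 to 0.8, one SB value, and no mean change after Week 12. Each rate is among subjects below the limit at the reference visit.

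| Mean rise by Week 12 (SD) | Upward shift from Day 1 | Upward shift from Week 12 | Day 1 shifts already present at Week 12 |
|---|---|---|---|
| 0.2 | 11.7–14.7% | 9.4–13.2% | 39–46% |
| 0.5 | 20.5–23.7% | 12.9–18.6% | 48–56% |
| 0.8 | 32.5–34.9% | 17.4–25.0% | 57–66% |

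The Week 12 column is not zero because values vary within subjects, so shifts in both directions need to be shown.

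*Weight.* This example assumes persistence. For an 80 kg subject the limit is 0.07 × 80 = 5.6 kg. A gain of 5.7 kg (5.7/80 = 7.1%) by Week 12 on 30 mg, then stable weight on 15 mg, is a PCI weight case in the 30/15 SB table with no change after the switch.

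**The case against.** Much of the other side stands:

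- **Adverse events already have a post-switch reference.** This covers SAEs, discontinuations and AESIs, and the AESIs include anemia, neutropenia, lymphopenia, renal dysfunction and hepatic disorders. A reader might infer that the plan cannot address the safety of the dose change; SAP 10.2 does not support that.
- **No planned number is wrong.** A change from Day 1 is correct for what it is labelled, and Protocol 7.5 asks for it. A reader might infer that the tables overstate the effect of escalation or give reduction the wrong sign. That happens only if cumulative change is read as change since the switch.
- **The laboratory PCI limits do not use Baseline.** Subject-level listings are planned for laboratory and vital-sign PCI cases, so onset should be checkable case by case. Protocol Table 3 calls for interruption at the same hemoglobin, neutrophil, lymphocyte and white-cell limits as Table D-1, which restricts carry-over there. It has no entry for lipids or CPK.
- **Weight enters only through Table D-4.** SAP 10.4 does not list it among the vital signs summarised as means.
- **A Week 12 reference does not isolate the switch.** Every SS1 non-responder escalates and every SS2 responder reduces, so no group with the same response stays on its dose.

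None of this supplies the missing displays. Listings do not replace counts, and neither the shift tables nor the CI for change since Week 12 can be derived from the planned summaries.

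**Conclusion.** The point holds in limited form. For Safety 2, the laboratory mean changes, laboratory and lipid shift tables, vital-sign mean changes and Table D-4 criteria describe the period since Day 1, and no companion display describes the period since the switch. Persisting absolute laboratory PCI values can be counted again under the new dose.

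This rests on reading Baseline as pre-treatment wherever the SAP uses the word without qualification in its laboratory and vital-sign analyses. Its size is unknown: the illustrations depend on assumed effects, on a plateau and reversibility for the means, and on persistence for the shifts and weight. It is a cheap improvement to a descriptive plan; no existing analysis needs to be replaced.

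**What to change.** In SAP 10.3, 10.4 and Appendix D:

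1. Define an SB Baseline as the last value on or before the first SB dose.
2. For Safety 2, by the four cohorts, add laboratory and vital-sign mean change with 95% CI from the SB Baseline, and shift tables from the SB Baseline.
3. Add counts of PCI values newly met or worsened relative to the SB Baseline.
4. Keep the existing from-Baseline tables and total PCI counts alongside.
5. State that change from Week 12 is uncontrolled and mixes the dose change with time on drug.

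No new data are needed: Protocol Appendix D already schedules laboratory tests, vital signs and body weight at Week 12. The cost is SAP wording, a second baseline flag in the datasets and additional tables.

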#### **Potentially Clinically Important Laboratory Values**

Laboratory abnormalities will be evaluated based on Potentially Clinically Important (PCI) criteria (NCI CTCAE V4.03 criteria of Grade 3 or above) in DB Period for the Safety 1, in SB Period for the Safety 2 Population and during the administration of upadacitinib for the All UPA Population. For each laboratory PCI criterion, the number and percentage of subjects who have a laboratory value meeting the criteria will be summarized. Listings will be provided to summarize subject-level laboratory data for subjects meeting PCI criteria. The PCI criteria are defined in Appendix D using CTCAE 4.03.

#### **Liver Function Tests**

For the purpose of assessing for potential Hy's law cases, the frequencies and percentages of subjects with post-baseline liver function test values that meet the PCI criteria (defined in Appendix D) will be presented in DB Period for the Safety 1 Population, in SB Period for the Safety 2 Population and during the administration of upadacitinib for the ALL UPA Population. A listing of possible Hy's Law cases will be provided.

### 10.4 Analysis of Vital Signs

Vital sign measurements of systolic and diastolic blood pressure, pulse rate, respiratory rate and body temperature will be summarized.

Each vital sign variable will be summarized for all time points (starting with Baseline) with the number of non-missing observations, mean and standard deviation, median, minimum and maximum. Mean change from Baseline to each applicable post-baseline visit in both DB Period and SB Period will be summarized for each vital sign variable, with the number of observations, Baseline mean, and visit mean. The change from Baseline mean, standard error, and 95% confidence interval will be presented for the mean change from Baseline within each treatment group in Safety 1 and Safety 2 Populations.

Vital sign variables will be evaluated based on potentially clinically important (PCI) criteria (Appendix D) for the Safety 1, Safety 2 and the ALL UPA Population. For each vital signs PCI criterion, the number and percentage of subjects who have at least one vital sign value meeting the criteria will be summarized. Listings will be provided to summarize subject-level vital sign data for subjects meeting PCI criteria.

10.5 Safety Topics of Interest

Not applicable.

10.6 Other Safety Analyses

Not applicable.

10.7 Safety Subgroup Analyses

Not applicable.

11.0 Other Analyses

Not applicable.

12.0 Interim Analyses

There will be no interim analyses.

#### 12.1 Data Monitoring Committee

Given no subjects participating in the study will receive placebo or other active comparators, the causality of any AEs reported in the participants can be adequately assessed in the context of upadacitinib treatment. The study team will monitor and evaluate any AEs to identify findings that could put the study participants at risk and then make clinical decisions regarding the study conduct, which could include modification or termination of the study. This can adequately safeguard the participants. Given the above, it is not necessary to implement an independent Data Monitoring Committee for the conduct of this study.

# 13.0 Overall Type-I Error Control

No hypothesis testing will be performed in this study. Overall type-1 error control is not considered.

[figure not shown]
# 14.0 Version History

Table 5. SAP Version History Summary

Version	Date	Summary
1.0	11 July 2023	Initial version
2.0	27 August 2024	
 
The other events of interest in version 1 have been reclassified into the AESI category. These events include Bone fractures, Retinal detachment, and Serious hypersensitivity reactions (in Section 3.4, 10.2.3, 10.2.4, 10.2.6 and Appendix B). These changes are due to the release of the PSSAP version 8.0 on Aug. 20, 2024.
 
Added the Rescue Definition as Appendix C.
 

		

2. Added the Rescue Definition as Appendix C.

3. Made some minor changes, including typo corrections

[figure not shown]
# 14.1 Changes to Planned Analyses in the Protocol

Not applicable

[figure not shown]

# **Appendix B.** Definition of Adverse Events of Special Interest

Adverse Events of Special Interest (AESI) will be identified using the following search criteria (**Note:** for each database lock, the categories of AESIs will follow the latest version of Product Safety Statistical Analysis Plan for Upadacitinib, with the exceptions of Hepatitis B Reactivation which is not an AESI. AESIs with the corresponding code for the current MedDRA version in that DBL will be shown in a summary table):

[figure not shown]

AESI	Type of MedDRA Query	Broad or Narrow Search	SMQ/CMQ Search Criteria
Serious Infections	CMQ		"Infections" – Subset for SAEs
Opportunistic Infection excluding tuberculosis and herpes zoster	CMQ		"Opportunistic Infection excluding tuberculosis and herpes zoster"
Possible malignancy	SMQ	Narrow	"Malignancies"
Malignancy	SMQ	Narrow	"Malignant Tumours"
Non-Melanoma Skin Cancer (NMSC)	SMQ/CMQ	SMQ Narrow	Skin Malignant Tumours (Narrow SMQ) removing Melanoma CMQ
Malignancy excluding NMSC			Malignancy Tumours Narrow SMQ and removing NMSC output
Lymphoma	SMQ	Broad	"Malignant Lymphomas"
Hepatic Disorder	SMQ	Narrow	"Drug Related Hepatic Disorders"
Adjudicated Gastrointestinal Perforations	Medical review of events identified by the "Gastrointestinal Perforation" SMQ Narrow search		
Anemia	CMQ		"Non-Hemolytic and Non- Aplastic Anemias"
Neutropenia	CMQ		"Hematological Toxicity – Neutropenia"
Lymphopenia	CMQ		"Hematological Toxicity – Lymphopenia (Upadacitinib Product Specific)"
Herpes Zoster	CMQ		"Herpes Zoster"
Renal Dysfunction	SMQ	Narrow	"Acute Renal Failure"

AESI	Type of MedDRA Query	Broad or Narrow Search	SMQ/CMQ Search Criteria
Active Tuberculosis	CMQ		"Active Tuberculosis"
Adjudicated cardiovascular events a	Output from CAC		
MACE*			
Cardiovascular Death			
Non-fatal Myocardial Infarction			
Non-fatal Stroke			
Other Adjudicated Cardiovascular Events			
Undetermined/Unknown Cause of Deaths			
Adjudicated Thrombotic Events	Output from CAC		
VTE**			
Deep Vein Thrombosis			
Pulmonary Embolism			
Other Venous Thrombosis			
Arterial Thromboembolic Events (non-cardiac, non- neurologic)			

- CAC Cardiovascular Adjudication Committee; CMQ company MedDRA query; PT preferred term; SMQ standard MedDRA query
- \* MACE: Major Adverse Cardiovascular Events, defined as cardiovascular death, non fatal myocardial infarction and non fatal stroke.
- \*\* VTE: Venous thromboembolic events, defined as deep vein thrombosis (DVT) and pulmonary embolism (PE) (fatal and non fatal).
- a. Reviewed and adjudicated by an independent Cardiovascular Adjudication Committee in a blinded manner.

